3. STUDY PLAN

3.1. Study Design

Overall Design

This single centre, randomized, crossover, proof-of-principle study will be a randomized four treatment, examiner blind [to the examiner performing the bite force & oral soft tissue (OST) examinations] design in subjects with well made and moderately well-fitting maxillary complete dentures. Informed consent will be obtained from participants before the implementation of any study procedure.

At the Screening Visit, subjects will be screened for eligibility and ability to perform the bite force manoeuvre according to stated inclusion/exclusion criteria. On the test day visit, subjects will report to the study site without adhesive placed in their dentures. Dentures will be removed and cleaned. An OST examination will be performed before the lower denture (if applicable) is secured using Super Poligrip® Flavour Free denture adhesive, whilst the upper denture is removed, and the pretreatment baseline incisal bite force measurements will be obtained (both practice bites and qualifying test bite). To maintain blinding, subjects must not disclose to the examiner if they are wearing adhesive or no adhesive. Subjects meeting all the inclusion criteria with no exclusions will then be randomized at Visit 2.

On each test day (Visits 2-5) subjects will undergo an OST examination and have their dentures cleaned. Denture adhesive treatment (or no treatment as per the randomization schedule) will then be applied by a member of study staff (ideally the same member of staff throughout the study) as per the application instructions, and the dentures worn by the subject. Incisal bite force measurements will be made at 0.5, 1, 3, 6, 9 and 12 hours after the dentures are placed in the mouth. After 0.5 hours assessment the subjects will be asked to complete questions about product ooze (Appendix II). The questions will be completed by the subjects themselves and these responses will then be given to study site staff to transfer to the eCRF.

Immediately following the last (12 hour) incisal bite force measurement, subjects will be asked to complete a short questionnaire relating to the after-taste and texture of the denture adhesive (Appendix III). This will be completed by the subject themselves in a quiet environment without external influence.

Immediately following subsequent upper denture removal by the subjects themselves, subjects will be asked to answer another short questionnaire (which will be

Document Name	Project CC protocol		
Туре	Version	Document Identifier	Effective Date
eldo clinical doc	5.0; Most-Recent; Effective; CURRENT	090032d580cfe581	23-Feb-2017 14:35:47
Reason For Issue	Auto Issue		

administered by the site staff; Appendix IV) pertaining to ease of removal of the denture when undertaking the treatment phases of the study, but not the negative no treatment control arm. The subjects will remove their dentures by themselves under supervision by site staff. Following denture removal, and completion of the associated questionnaire, site staff will clean the denture before returning to the patient at the end of the study.

These assessments will be followed by the final post-treatment OST examination.

These procedures will be repeated in a crossover manner. There will be at least 24 hours (up to 14 days) between treatment visits to allow recovery from the bite force procedures.

Visit 1 - Screening Visit

The following assessments will be conducted in the order written:

- Written informed consent.
- Demographics, medical history, current/concomitant medications, and dental history.
- Criteria for well made dentures
- Inclusion/exclusion criteria
- Oral soft tissue examination including edentulous maxillary arch
- Denture bearing tissue score
- Kapur Index assessment
- Denture cleansing
- Mandibular denture stabilization (with adhesive, if deemed to be necessary to ensure accurate bite force measures; at the discretion of the Investigator)
- Three incisal bite force readings with no adhesive on upper denture (for training)
- Incisal bite force with no adhesive on the upper denture (qualifying)
- Inclusion/exclusion criteria (following initial bite force measures)
- Subject eligibility
- Adverse events and incident reporting (assessed from the OST

 EXAMINATION AT SCREENING start of the first bite force measurement)

Visits 2, 3, 4 & 5

The following assessments will be conducted:

- Review of current/concomitant medications, adverse events and incidents
- Oral soft tissue examination including edentulous maxillary arch
- Denture cleansing
- Mandibular denture stabilization (with adhesive, if deemed to be necessary to

Document Name	Project CC protocol		
Туре	Version	Document Identifier	Effective Date
eldo clinical doc	5.0; Most-Recent; Effective; CURRENT	090032d580cfe581	23-Feb-2017 14:35:47
Reason For Issue	Auto Issue		

ensure accurate bite force measures; at the discretion of the Investigator)

- Three incisal bite force readings with no adhesive on the upper denture (for practice)
- Incisal bite force with no adhesive on the upper denture (pre-treatment "baseline")
- Subject eligibility
- Adverse events and incident reporting (assessed pre bite force measurement)
- Continued eligibility
- Randomisation (Test/Treatment day 1 only)
- Weigh maxillary denture prior to adhesive placement
- Product application by site staff to maxillary denture (or no adhesive for the no adhesive negative control)
- Weigh maxillary denture immediately following adhesive placement (record weight difference i.e. weight of adhesive used to ensure correct dose applied)
- Dentures of subjects randomized to a denture adhesive shall be weighed before & after adhesive application
- Upper denture insertion by subject
- Incisal bite force measurements (at 0.5 hours prior to product ooze questionnaire (Appendix II), followed by 1, 3, 6, 9 & 12 hours post adhesive application)
- Subject evaluation questionnaire (product ooze) 0.5 hours post adhesive application (Appendix II)
- Subject sensory questionnaire (flavour, texture and extrusion of the adhesive from the tube; Appendix III) immediately following the last (12 hr) bite force measure whilst upper denture still retained in the mouth
- Removal of denture from the mouth by the subject
- Denture adhesive retention questionnaire completed by Examiner/ site staff
- Removal of excess adhesive from the mouth by the subject facilitated by site study staff as and where necessary
- Subject denture removal questionnaire (Appendix IV) immediately following 12 hour post adhesive application bite force measure, completion of subject sensory questionnaire and subsequent removal of the upper denture
- Study Staff to check denture removal questionnaire completion to ensure that
 any potential AEs which may have been noted in the questionnaire free text is
 reviewed and captured in the eCRF before the subject leaves the site
- Post-treatment OST by a blinded examiner
- Dentures cleaned and returned to subject
- Adverse events and incident reporting (assessed post bite force measurement)

There will be at least 24 hours (up to 14 days) between subsequent treatment days to

Document Name	Project CC protocol	CC protocol	
Туре	Version	Document Identifier	Effective Date
eldo clinical doc	5.0; Most-Recent; Effective; CURRENT	090032d580cfe581	23-Feb-2017 14:35:47
Reason For Issue	Auto Issue		

allow recovery from the bite force procedures.

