3.2. Subject Restrictions

Lifestyle/ Dietary

During the entire study (screening to LSLV):

- Subjects will be instructed to report to the clinic on the treatment visit days
 without the presence of denture adhesive in either their maxillary or
 mandibular denture.
- Subjects will be required to remain on site for the duration of the treatment visit day. Standardized meals will be provided.
- On the test days, subjects' intake of hot & cold liquids will be restricted.
- Smoking, including e-cigarettes and the use of chewing tobacco or other tobacco products are prohibited for the duration of screening and on each test day.
- If subjects were using denture adhesives to stabilize their dentures, then they
 can continue using the denture adhesives during the washout periods between
 treatment visits only, but they cannot change it during the course of the study.
- Subjects should not consume any food or liquid an hour before the treatment visit. Subjects can consume small sips of water for medications.
- Subjects are not permitted to chew gum throughout the study.

Medications and Treatments

During the entire study (screening to LSLV):

- The details of current and concomitant medications will be collected and subjects will be allowed to participate if these medications are judged to be non-interfering by the investigator.
- Subjects will not be permitted to have any dental/denture work performed during the time that they are in the study, unless discussed and permitted by the examiner. This is to assure that the denture fit will not be altered during the study.

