4. DIAGNOSIS

Document Name	Project CC protocol		
Туре	Version	Document Identifier	Effective Date
eldo clinical doc	5.0; Most-Recent; Effective; CURRENT	090032d580cfe581	23-Feb-2017 14:35:47
Reason For Issue	Auto Issue		

- a. Completely edentulous maxillary arch restored with a conventional full acrylic based upper complete denture.
- b. Dentate, partial or full edentulous mandibular arch. Partial or full edentulous arch may be restored with a stable complete, partial or implant supported denture.
- c. Maxillary dentures must be considered to be moderately well-fitting at the screening visit (Kapur Index, Olshan Modification: retention score ≥2, stability score ≥2).
- d. Maxillary dentures and mandibular dentures, if present, must be considered to be well-made based on design and construction criteria specified in the protocol.
- e. The qualifying maxillary incisal bite force readings (without adhesive) must be less than or equal to 9 pounds at the Screening Visit and subsequent visit pre-treatment baseline bites.
- f. At least 2 of the 4 qualifying bite readings at the Screening Visit must be reproducible (±2lb). At subsequent visits the bite force readings must be within ±2lb for 1 of the 3 practice bites and the pre-treatment baseline bite.

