6.1.9. Kapur (Olshan Modification) Denture Retention & Stability Assessment

At the screening visit, the examiner will determine the subject's denture retention and stability score and it will be recorded in the CRF.

Retention Criteria

With gloved hands, the examiner will attempt to unseat the maxillary complete denture by applying an opposing vertical force at the canine/lateral incisor region of the denture. The examiner will score **retention** as 0 - 5 using the following criteria:

- 5= Excellent- denture offers excellent resistance to vertical pull and lateral force
- 4= Very Good- denture offers very good resistance to vertical pull and lateral force
- 3= Good- denture offers moderate resistance to vertical pull and lateral force
- 2= Fair- denture offers moderate resistance to vertical pull and little or no resistance to lateral forces
- 1= Poor- denture offers slight resistance to vertical pull and little or no resistance to lateral force

Document Name	Project or protocol		
Туре	Version	Document Identifier	Effective Date
eldo clinical doc	5.0; Most-Recent; Effective; CURRENT	090032d580cfe581	23-Feb-2017 14:35:47
Reason For Issue	Auto Issue		

0= No retention- when the denture is seated in place, it displaces itself

Stability Criteria

With gloved hands, the examiner will attempt to rock the seated dentures by placing alternate horizontal force at the cuspid and contralateral molar regions of the maxillary complete dentures. The examiner will score denture **stability** as 0-4 using the following criteria:

- 4= Excellent- when denture base offers no rocking on its supporting structures under pressure
- 3= Good- when denture base has very slight rocking on its supporting structures under pressure
- 2= Fair- when denture base has slight rocking on its supporting structures under pressure
- 1= Poor- when denture base has moderate rocking on its supporting structures under pressure
- 0= No stability- when denture base has extreme rocking under pressure

Following completion of informed consent (section 6.1.2), medical history/concomitant medication (section 6.1.4), dental history (section 6.1.5), well-made denture assessment (section 6.1.6), OST examination (section 6.1.7) and Kapur index/assessment (section 6.1.9), subject inclusion/exclusion will be determined as per the inclusion/exclusion criteria (section 4).

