6.1.10. Denture cleansing

Dentures should be removed from the mouth by the subject. Denture cleansing should be performed by suitably qualified site staff. Enough denture cleansing paste will be applied to the supplied denture brush. Holding the upper (and lower where necessary) all surfaces of the dentures will be thoroughly cleaned to remove all traces of denture fixative, plaque and particulates/debris. The dentures will then be rinsed thoroughly with running water. Dentures should then be dried using clinical paper towels prior to denture adhesive application. Please note that the denture cleansing paste is to be used extra-orally and not for use in the mouth. Hands should be washed thoroughly following application and use of the denture cleansing paste.

Document Name	Project or protocol		
Туре	Version	Document Identifier	Effective Date
eldo clinical doc	5.0; Most-Recent; Effective; CURRENT	090032d580cfe581	23-Feb-2017 14:35:47
Reason For Issue	Auto Issue		

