6.1.14. Bite Force Measures at Screening

At Screening, subjects will have any denture adhesive on their denture removed. A member of site staff (trained in bite force procedures) will instruct the subjects in the execution of the bite force procedure participation. The subject will be instructed to sit and hold his/her head in a natural position so that the occlusal plane is parallel to the floor. The examiner will stand or sit in front of the subject holding the bite force transducer parallel to the floor at a comfortable level for the subject. In order to facilitate insertion the examiner may angle the bite force plates for certain subjects as necessary. The examiner will prevent cross contamination by placing a clean finger cot over the bite force plates for each subject in addition to a clean infection control sleeve over the transducer hand piece. The examiner will insert the bite force plates into the subject's mouth, which may be customized using impression material in

Document Name	Project Col protocol		
Туре	Version	Document Identifier	Effective Date
eldo clinical doc	5.0; Most-Recent; Effective; CURRENT	090032d580cfe581	23-Feb-2017 14:35:47
Reason For Issue	Auto Issue		

order to facilitate anterior denture tooth placement on the bite force transducer. The examiner will instruct the subject to swallow, and then ensure that the muscles of mastication are relaxed. The examiner will signal the subject to bite until he/she feels movement on the maxillary denture at which time he/she will be instructed to release the bite plate. If, in the opinion of the examiner, the subject will be unable to successfully complete the required bite force system training tasks, the subject will be withdrawn from the study.

During the Screening Visit, the examiner will record a triplicate bite force measurement at pre-treatment baseline without denture adhesive. These will be referred to as "training bites" on the CRF as the subject becomes accustomed to the equipment. Four (4) further bites will be made; 2 of these 4 'qualifying' bites must be reproducible (±2lb) for a subject to be eligible to the study. All 4 of the "qualifying" bites must be less than or equal to 9 pounds. These will form the subject eligibility/ adherence for continuation in the study.

6.2. Visits 2, 3, 4 & 5

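### At screening, denture fit is scored before the denture is cleansed, and no rule requires the denture to be free of adhesive when it is scored

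*Protocol*

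**What the plan says.** The Visit 1 list in Protocol 3.1 opens with "The following assessments will be conducted in the order written", and SAP section 3 repeats the heading and the list. The seventh item is "Kapur Index assessment" and the eighth is denture cleansing. Section 6 describes them in the same order, as 6.1.9 and 6.1.10.

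The fit criterion is inclusion 4c: "Maxillary dentures must be considered to be moderately well-fitting at the screening visit (Kapur Index, Olshan Modification: retention score ≥2, stability score ≥2". Protocol 6.1.9 describes how the examiner pulls on and rocks the denture, and says that after the "Kapur index/assessment (section 6.1.9), subject inclusion/exclusion will be determined as per the inclusion/exclusion criteria (section 4". It does not mention the state of the denture.

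Adhesive comes off under 6.1.10, where "all surfaces of the dentures will be thoroughly cleaned to remove all traces of denture fixative, plaque and particulates/debris". Protocol 6.1.14 adds: "At Screening, subjects will have any denture adhesive on their denture removed". On arrival, Protocol 3.2 says "Subjects will be instructed to report to the clinic on the treatment visit days" with no adhesive in either denture. It gives no such instruction for screening.

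**The concern.** The Kapur retention score grades how well the denture resists a vertical pull and lateral force. The Introduction names increased retention as a primary benefit of adhesive. A score taken with adhesive or residue in place can therefore overstate how well the bare denture fits.

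What is at stake is who the trial is about. The Introduction contrasts earlier bite-force studies in clinically poor dentures with this trial's moderately well-fitting ones, and Protocol 3.4 says that only well-fitting dentures may be included. A subject who scored 2 with adhesive but would score 0 or 1 without it would still have met 4c as written. That subject would not be recorded as an eligibility violation, so the per-protocol rules in SAP 5.1 would not remove the data on that ground.

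**Working it through.** No arithmetic in the plan bears on this point. The plan's one design calculation, about 81% power with 18 completers, does not enter the argument. The check is to set the provisions side by side.

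| Provision | Place relative to Kapur at screening | Adhesive condition |
|---|---|---|
| Arrival rule, Protocol 3.1 and 3.2 | Does not apply: test or treatment days only | None for screening |
| Well-made assessment, soft tissue examination, tissue score (6.1.6 to 6.1.8) | Before | None stated |
| Kapur assessment (4c, 6.1.9) | The step itself | None stated |
| Denture cleansing (6.1.10) | Directly after | All adhesive removed |
| Qualifying bite force (4e, 6.1.14) | After | No adhesive |
| Visits 2 to 5 | Kapur not scheduled | Not applicable |

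**Step 1: can adhesive be present at screening?** Yes. Protocol 3.2 provides for subjects who already use adhesive, and 6.1.14 speaks of removing any that is on the denture.

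**Step 2: does anything remove it before Kapur?** No text does. The two provisions that remove adhesive, 6.1.10 and 6.1.14, both come after 6.1.9.

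**Step 3: is the adhesive state left open on purpose?** Nothing suggests so. In the same list of criteria, 4e says: "The qualifying maxillary incisal bite force readings (without adhesive) must be less than or equal to 9 pounds". The condition is written out for bite force and absent for fit.

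**Step 4: how much help would change eligibility?** One grade. Retention 1 means slight resistance to vertical pull and fails. Retention 2 means moderate resistance and passes. Both grades have little or no resistance to lateral force.

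**Step 5: would a later step catch it?** No.
- Kapur appears only in the Visit 1 column of the Schedule of Events.
- The second eligibility check at screening follows the bite-force readings and adds no new Kapur score.
- Criterion 4e is an upper limit of 9 lb, and 4f asks for reproducibility within 2 lb. Neither sets a minimum.
- The well-made assessment concerns design and construction.

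**Step 6: does it reach the treatment comparison?** Not directly. Each subject is their own control. At Visits 2 to 5 the dentures are cleansed first, and the baseline bite is taken with no adhesive on the upper denture.

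**The case against.** The strongest reply is that the denture will have been out of the mouth before Kapur is scored. The well-made assessment looks at the tissue surfaces, the soft tissue examination covers the hard palate and the edentulous maxilla, and the tissue score rates the ridge under the denture. Any bond formed at home would be broken, and adhesive on the fitting surface would be seen. This makes a full-strength adhesive effect less likely. It does not settle the matter, because no text has the denture cleaned before it is reseated, and staff who cleaned it on their own initiative would depart from the written order.

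A second reply is that the sentence in 6.1.14 on removing adhesive is worded for the whole Screening Visit. It is, but it stands in the bite-force section and gives no earlier timing, so it does not clearly protect the Kapur score. Likewise, 3.2 allows a subject's own adhesive only between treatment visits, under a heading that runs from screening onward. That does not say how a subject must arrive at screening.

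A third reply is that the ordered list cannot be followed literally: it names the inclusion and exclusion criteria before the examinations on which they depend. That is fair. It weakens the list as a strict sequence, but 6.1.9 and 6.1.10 keep the same order and nothing states the opposite one. The Synopsis list and the Schedule of Events do not govern sequence, and this point does not rest on them.

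A reader might go further and infer that enrolment would shift towards poorly fitting dentures, or that the trial could not answer its question. The documents do not support that: they do not say how many subjects would arrive with adhesive, or how much residue would raise a score. Kapur is also an examiner's rating, so it is the only scored fit criterion rather than an objective one.

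**Conclusion.** The point holds as a gap in the screening procedure. A site that follows the plan as written can apply criterion 4c to a denture that still carries the subject's own adhesive or residue, and no later step would reveal it.

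Its size cannot be estimated. The number affected lies somewhere between none and all of the roughly 21 randomized subjects. It is limited to those who attend with adhesive and whose bare denture would score below 2 on retention or stability. This shows a possibility, not a frequency.

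The conclusion rests on two assumptions: that some subjects attend screening with adhesive, and that residue can raise the score by a grade once the denture has been taken out and reseated. The consequence is confined to how well the enrolled subjects match the stated population. Bias in the test-versus-control contrast does not follow. The point is worth correcting because the correction is cheap, not because the primary analysis is in danger.

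**What to change.** In the ordered Visit 1 lists of Protocol 3.1 and SAP section 3, move denture cleansing ahead of the Kapur Index assessment. In Protocol 6.1.9, and in criterion 4c, state that retention and stability are scored on the cleaned maxillary denture with no adhesive. The Synopsis and Schedule of Events may be aligned for consistency.

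Extending the arrival restriction in 3.2 to screening is not needed. Subjects come to that visit before they have consented, and cleansing before scoring makes their state on arrival immaterial.

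The cost is amendment wording: no new procedure, staff or visit. The protocol's amendment section treats changes to selection criteria in an ongoing study as substantial, so the sponsor should settle how the added words in 4c are classified. The practical downside is that a few more adhesive users may fail screening, against a plan to screen about 25 in order to randomize about 21.
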